## 5. METHODS AND PROCEDURES

### 5.1. Study Procedures

- Study personnel will complete the electronic **Screening Log** to monitor all subjects approached for participation in this study, the outcome of the assent/consent process (declined or enrolled), and reason for declining participation.
- Study Personnel will complete the **Eligibility Checklist** for each pair of subjects who provide assent and consent for participation in this study.
- **Washout Period:** Patients who are already taking tacrolimus (i.e., Protopic), crisaborole (i.e., Eucrisa), or any steroid- sparring medication for atopic dermatitis are eligible for the study if he/she agrees to discontinuation of the medication for two weeks (i.e., 14 days) prior to starting study procedures. If the patient agrees to the two week "washout period", assent and informed consent can be obtained during that clinic visit. A study visit will be scheduled for the patient and caregiver at a convenient time at least two weeks (i.e., 14

days) from the day of assent/consent. After the two week “washout period”, the subject will return to clinic for the baseline study visit and be randomized to tacrolimus 0.03% or crisaborole. The subject will either be given a tube of tacrolimus 0.03% or crisaborole. All study procedures will continue as described below starting with the **ASPIRE On-study Form**.

- Assent and informed consent are obtained from each subject, without coercion, prior start of any study procedures. Assent Form 1 will be used for subjects ages 8 to 12 years and Assent Form 2 will be used for subjects ages 13 to 15 years. Informed consent will be completed by the parent/adult caregiver. The caregiver subject will provide their name, mailing address, and signature on the **Study Reimbursement Form**. Each subject (child and adult) will complete a W9 form for study reimbursement.
- Study personnel will notify the caregiver that they will be contacted by phone for reminders about upcoming study appointments and screening for any adverse reactions. Study personnel will ask if leaving a voicemail message is okay in case a call is missed. This information will be kept in a password-protected excel file **Call Log** located in the study folder on the Dermatology CTU’s University sharedrive. Study personnel will only have access to this study folder and the excel file.
- Study personnel will add appropriate subject information and study progress to the **Comprehensive Study Log**, as required by RSRB. This log is a password-protected excel file located in the study folder on the Dermatology CTU’s University sharedrive. Study personnel will only have access to this study folder and excel file.
- Subjects will be on study for at least 12 weeks. Subjects will be assessed at three different time points (Baseline, 6 Weeks, and 12 Weeks). Each assessment will be performed in the dermatology clinic and take approximately 30 minutes or less
- Pediatric subjects will be randomized 1:1 to one of two topical treatments: crisaborole or tacrolimus 0.03%. Both of these topical treatments are standard care for mild to moderate atopic dermatitis. Study personnel will obtain randomization in REDCap. After randomization, the treating dermatologist (i.e., [REDACTED]) will prescribe crisaborole or tacrolimus 0.03% to the pediatric subject for treatment of atopic dermatitis. Study personnel will dispense a tube of tacrolimus 0.03% or crisaborole to the subject based on randomization. The topical treatments will be applied to all affected areas twice daily for at least 12 weeks on this study. Additional tubes of tacrolimus 0.03% or crisaborole will be dispensed to the subject if needed to complete the 12 week treatment and assessment period. At the completion of the study, the treating dermatologist may continue or change the prescribed treatment for atopic dermatitis.
- Study personnel will complete the **ASPIRE On-Study Form** in REDCap. This form collects demographic information on both the pediatric subject and caregiver subject. Additionally, the form collects treatment information related to atopic dermatitis, all current medications, and medical history for the pediatric subject. This form will be completed after assent and consent are obtained.

- **Baseline Assessment:**
  - *Study personnel:* Trained study personnel (MD/NP) will perform Eczema Area & Severity Index (EASI), Investigator Static Global Assessment (ISGA), and Percentage Body Surface Area (%BSA) for the severity of atopic dermatitis. Study personnel will also weigh the tube of crisaborole and tacrolimus 0.03% prior to distribution to the subject. Study personnel will have an average weight for tube of tacrolimus prescribed. Study personnel will enter EASI, ISGA, and tube weight into the electronic **Assessment Form (Baseline)** in REDCap.
  - *Pediatric Subjects:* Pediatric subjects ( $\geq 5$  years) will complete five self-report outcome measures (**PROMIS® Itch, PROMIS® Pain Interference, Children's Dermatology Life Quality Index (CDLQI), PROMIS® Anxiety, PROMIS® Depression**) on an iPad. All self-report measures can be completed with the assistance of their parent or guardian. All five self-report outcome measures can be completed in 20 minutes or less. Pediatric subjects  $< 5$  years will not complete any self-report measures on the iPad.
  - *Caregiver Subjects:* All caregivers will complete one self-report questionnaire about their child's sleep habits (**Children's Sleep Habits Questionnaire (CSHQ)**) and two self-report measures for caregiver burden (**Caregiver Burden Inventory (CBI)**) and quality of life (**Family Dermatology Life Quality Index (FDLQI)**) on an iPad. All self-report measures can be completed in 5 minutes.
- Pediatric subjects will complete a Pediatric Subject Reimbursement Form at the end of the Baseline Assessment. The pediatric subject will print their name, address, sign and date the form. The adult caregiver may help the child complete the form if he/she has difficulty writing. Pediatric subject  $\geq 5$  years must sign the form. Study personnel will give the pediatric subject a \$10 gift card after for the completion of this form for completion of the Baseline Assessment. For pediatric subjects  $< 5$  years, the adult caregiver will complete and sign the form. Study personnel will give the adult caregiver subject a \$10 gift card after for the completion of this form for completion of the Baseline Assessment.
- Study personnel will call the caregiver by phone during the Week 3 of treatment for adverse event monitoring of their child who is participating and on topical treatment. Study personnel will ask: 1) Has your child been able to use the topical treatment without any problems?; 2) Has your child experienced any burning from the topical treatment?; and 3) Has your child experienced any side effects or adverse reactions while using the topical treatment?. Study personnel will document the phone call in the Call Log. Adverse events will be documented on AE source doc.
- Study personnel will call the caregiver by phone at least 48 hours prior to the 6 Week Assessment to remind he/she of their upcoming appointment and to bring their tube of topical treatment with them to the appointment. Study personnel will also monitor for

adverse events by asking: 1) Has your child been able to use the topical treatment without any problems?; 2) Has your child experienced any burning from the topical treatment?; and 3) Has your child experienced any side effects or adverse reactions while using the topical treatment?. Study personnel will document the phone call in the Call Log. Adverse events will be documented on AE source doc.

- **6 Week Assessment:**

- This assessment should occur 6 weeks ( $\pm 7$  days) after the start of topical treatment (i.e., after Baseline Assessment). This study visit may be performed by telemedicine (i.e., zoom visit) if deemed appropriate and preferred by physician and subject. All currently scheduled and enrolled subjects will be given the option to have a study visit performed by telemedicine or in clinic. Study personnel will contact the enrolled subjects with scheduled 6 week and 12 week study visits by phone to ask if the subject would prefer to keep their in clinic study visit or have the study visit by telemedicine (zoom visit). All visits will be scheduled at a convenient time for the subject.
- **Study personnel:** Trained study personnel (MD/NP) will perform EASI and ISGA for the severity of atopic dermatitis. Study personnel will also weigh the tube of crisaborole and tacrolimus 0.03% prior to distribution to the subject. Study personnel will enter the EASI, ISGA, and tube weight into the electronic **Assessment Form (6 Week)** in REDCap.
- **Pediatric Subjects:** Pediatric subjects  $\geq 5$  years will complete five self-report outcome measures (**PROMIS® Itch, PROMIS® Pain Interference, Children’s Dermatology Life Quality Index (CDLQI), PROMIS® Anxiety, PROMIS® Depression**) on an iPad. All self-report measures can be completed with the assistance of their parent or guardian. All five self-report outcome measures can be completed in 20 minutes or less. Pediatric subjects  $<5$  years will not complete any self-report measures on the iPad.
- **Caregiver Subjects:** All caregivers will complete one self-report questionnaire about their child’s sleep habits (**Children’s Sleep Habits Questionnaire (CSHQ)**) and two self-report measures for caregiver burden (**Caregiver Burden Inventory (CBI)**) and quality of life (**Family Dermatology Life Quality Index (FDLQI)**) on an iPad. All self-report measures can be completed in 5 minutes.
- Pediatric subjects will complete a Pediatric Subject Reimbursement Form at the end of the 6 Week Assessment. The pediatric subject will print their name, address, sign and date the form. The adult caregiver may help the child complete the form if he/she has difficulty writing. Pediatric subject  $\geq 5$  years must sign the form. Study personnel will give the pediatric subject a \$10 gift card after for the completion of this form for completion of the 6 Week Assessment. For pediatric subjects  $<5$  years, the adult caregiver will complete and sign the form. Study personnel will give the adult caregiver subject a \$10 gift card after for the completion of this form for completion of the Baseline Assessment.

- Study personnel will call the caregiver by phone during the Week 9 of treatment for adverse event monitoring of their child who is participating and on topical treatment. Study personnel will ask: 1) Has your child been able to use the topical treatment without any problems?; and 2) Has your child experienced any side effects or adverse reactions while using the topical treatment?. Study personnel will document the phone call in the Call Log. Adverse events will be documented on AE source doc.
- Study personnel will call the caregiver by phone at least 48 hours prior to the 6 Week Assessment to remind he/she of their upcoming appointment and to bring their tube of topical treatment with them to the appointment. Study personnel will also monitor for adverse events by asking: 1) Has your child been able to use the topical treatment without any problems?; and 2) Has your child experienced any side effects or adverse reactions while using the topical treatment?. Study personnel will document the phone call in the Call Log. Adverse events will be documented on AE source doc.
- **12 Week Assessment:**
  - This assessment should occur 6 weeks ( $\pm 7$  days) after the 6 Week Assessment (i.e., 12 weeks after Baseline Assessment). This study visit may be performed by telemedicine (i.e., zoom visit) if deemed appropriate and preferred by physician and subject. All currently scheduled and enrolled subjects will be given the option to have a study visit performed by telemedicine or in clinic. Study personnel will contact the enrolled subjects with scheduled 6 week and 12 week study visits by phone to ask if the subject would prefer to keep their in clinic study visit or have the study visit by telemedicine (zoom visit). All visits will be scheduled at a convenient time for the subject.
  - *Study personnel:* Trained study personnel (MD/NP) will perform EASI and ISGA for the severity of atopic dermatitis. Study personnel will also weigh the tube of crisaborole and tacrolimus 0.03% prior to distribution to the subject. Study personnel will enter the EASI, ISGA, and tube weight into the **electronic Assessment Form (12 Week)** in REDCap.
  - *Pediatric Subjects:* Pediatric subjects  $\geq 5$  years will complete five self-report outcome measures (**PROMIS® Itch, PROMIS® Pain Interference, Children's Dermatology Life Quality Index (CDLQI), PROMIS® Anxiety, PROMIS® Depression**) on an iPad. All self-report measures can be completed with the assistance of their parent or guardian. All five self-report outcome measures can be completed in 20 minutes or less. Pediatric subjects  $<5$  years will not complete any self-report measures on the iPad.
  - *Caregiver Subjects:* All caregivers will complete one self-report questionnaire about their child's sleep habits (**Children's Sleep Habits Questionnaire (CSHQ)**) and two self-report measures for caregiver burden (**Caregiver Burden Inventory (CBI)**) and quality of life (**Family Dermatology Life Quality Index (FDLQI)**) on an iPad. All self-report measures can be completed in 5 minutes.

- Pediatric subjects will complete a Pediatric Subject Reimbursement Form at the end of the 12 Week Assessment. The pediatric subject will print their name, address, sign and date the form. The adult caregiver may help the child complete the form if he/she has difficulty writing. Pediatric subject  $\geq 5$  years must sign the form. Study personnel will give the pediatric subject a \$10 gift card after for the completion of this form for completion of the 12 Week Assessment. For pediatric subjects  $<5$  years, the adult caregiver will complete and sign the form. Study personnel will give the adult caregiver subject a \$10 gift card after for the completion of this form for completion of the Baseline Assessment.
- After completion of study procedures, the adult caregiver will be reimbursed for their study participation. Subjects completing all study procedures will be reimbursed \$100. Reimbursement will be pro-rated to reimburse subjects for any and all of their study participation (i.e., \$20 for completion of Baseline Assessment; \$40 for completion of 6 Week Assessment; and \$40 for completion of 12 Week Assessment. A check will be mailed by University of Rochester to the adult caregiver at the address provided on the Study Reimbursement Form for their participation in this study.
- After study procedures are completed, the child's treatment of atopic dermatitis will continue as deemed appropriate by the treating dermatologist.

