### **1.2. Background**

AD can have detrimental impacts on overall quality of life for both patients and their families. PROs provide an efficient way to monitor the impact of disease and effect of treatment(s) on patients' physical, mental, and social health. Additionally, PROs can elucidate the impact of the disease on caregivers and families. Topical corticosteroids have been recommended as the first line treatment for AD, but their chronic use is associated with adverse effects, including dyspigmentation, telangiectasias, acne, and skin atrophy (5). Crisaborole (Eucrisa™) is a recently approved nonsteroidal topical ointment for the treatment of patients ( $\geq 2$  yrs of age) with mild to moderate AD. Crisaborole has a novel mechanism of action by inhibiting the phosphodiesterase-4 enzyme which has been shown to be elevated in AD leukocytes and is thought to be responsible for the tissue inflammation observed in this disease. Like tacrolimus, which has a different mechanism of action (e.g. calcineurin antagonist), it provides a safer alternative to topical steroids, which is especially relevant for children with AD. Unfortunately, it can be difficult to obtain prior authorization for this new medication. In contrast, tacrolimus 0.03% ointment is now available as a generic and is therefore much easier to prescribe because more insurance companies cover it for children (2-15yrs of age) with moderate AD. Many clinicians believe crisaborole to be more effective than tacrolimus; however long-term comparator studies have not been done. Paller *et al* showed that crisaborole was better than vehicle in children and adults with AD; however no baseline secondary measures (e.g., pruritus, signs of AD) were reported (5, 6). Nevertheless, recent post-hoc analysis of Phase 3 crisaborole studies observed a very early reduction in itch that may have a significant effect on patient and caregiver PROs (7) providing a potential advantage for crisaborole. This study will use a series of PROs to monitor the treatment effects of crisaborole and tacrolimus 0.03% over a 12 week period of time. The treatment for a chronic inflammatory disease characterized by flares and remissions must be longer than 30 days (i.e., 1 month) (5). We anticipate that crisaborole will

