### 1.4 Objectives

**Primary Objective:** To investigate the effect of crisaborole (Eucrisa™) treatment on patient-reported itch and pain in patients with mild to moderate atopic dermatitis compared to tacrolimus 0.03%.

- *Hypothesis:* We hypothesize that crisaborole (Eucrisa™) treatment will significantly decrease (i.e., score change  $\geq 5$ ) the severity of itch and pain over time and these changes will correlate with improvements Eczema Area and Severity Index (EASI) in atopic dermatitis. We further hypothesize that the improvement in these PROs will be greater in the crisaborole treated subjects compared to those receiving tacrolimus.
- *Primary Outcome Measures:* Change in PROMIS® Itch and PROMIS® Pain Interference measures after 12 weeks of treatment.

**Secondary Objective:** To investigate the effect of crisaborole (Eucrisa™) treatment on patient-reported quality of life, sleep, anxiety, and depression in patients with mild to moderate atopic dermatitis compared to tacrolimus 0.03%.

- *Hypothesis:* We hypothesize that crisaborole (Eucrisa™) treatment will improve quality of life and decrease (i.e., score change  $\geq 5$ ) the severity of one or more of the PROs (sleep, anxiety, or depression). These changes will correlate with improvements in atopic dermatitis (EASI). We also hypothesize that the improvement in these PROs will be greater in the crisaborole treated subjects compared to those receiving tacrolimus.
- *Secondary Outcome Measures:* Change in Children’s Dermatology Life Quality Index (CDLQI), PROMIS® Anxiety, PROMIS® Depression, and Children’s Sleep Habits Questionnaire (CSHQ) after 12 weeks of treatment.

**Tertiary Objective:** To elucidate the impact of crisaborole (Eucrisa™) treatment or tacrolimus 0.03% on caregiver burden.

- *Hypothesis:* We hypothesize that improvements in caregiver burden will correlate with improvements in atopic dermatitis (EASI), as well as decreased severity in PROs.
- *Tertiary Outcome Measures:* Change in Caregiver Burden Inventory and Family Dermatology Life Quality Index (FDLQI) after 12 weeks of treatment.

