### 3.5. Inclusion Criteria:

#### Pediatric Subjects:

- a) Male and female subjects of inclusive ages of 2 to 15 years at screening visit.

- b) Diagnosis of  $\leq$ moderate atopic dermatitis or eczema (ISGA 2 or 3 and  $\geq 3\%$  BSA, excluding scalp).
- c) If subject is taking or prescribed antihistamines, subject must be on stable dose of antihistamines.
- d) If subject is taking topical steroids, subject must be on stable dose of topical steroid.
- e) Subjects currently taking tacrolimus (i.e., Protopic), crisaborole (i.e., Eucrisa), or other topical steroid-sparring medications are eligible for this study if he/she agrees to a two week “washout period” prior to starting study procedures (See “washout period” described below on page 9).
- f) If subject is taking systemic anti-inflammatory therapy (i.e., cyclosporine, etc), subject must be on a stable dose of the systemic anti-inflammatory medication for at least six week prior to enrollment and it must be anticipated that this dose would not change during their participation in this study, unless deemed medically necessary. Any changes in medication dose due to flaring of atopic dermatitis or side effects will be documented on the *AD Flare Medication Form* and *AE Source Doc* (see page 19).
- g) Caregiver (i.e., adult parent or guardian) must agree to participate in the study with the patient.
- h) Subject must be able to read and speak English.
- i) Subject, ages  $\geq 8$  years, is able to give assent.

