*Comprehensive Study Log:* This is a password-protected excel spreadsheet that contains a log for all subjects in the study. The information kept in this file include: Subject Pair ID, Caregiver Name, AD Patient Name, AD Patient MRN, Screened & Eligible, Assent Completed, Consent Completed, Screen Fail, Baseline Complete, 6 Week Complete, 12 Week Complete, Completed Study, Withdrawal, Loss to Follow-up, and Topical Treatment. Study personnel will complete the required subject information and check the appropriate boxes as the study progresses to monitor subject participation in the study.

*ASPIRE On-Study Form:* This form captures demographic information on both the caregiver and patient subjects, as well as relevant clinical information for the patient subjects. This form will be completed electronically and submit information directly to the secure REDCap database at the University of Rochester Medical Center. This form will collect the following:

- Subject Pair ID
- On Study Date
- Washout Period Required (yes/no)
- Caregiver Initials
- Relation of Caregiver
- Caregiver Gender
- Caregiver Age
- Caregiver Race
- Caregiver Ethnicity
- AD Patient Initials
- AD Patient Gender
- AD Patient Race
- AD Patient Ethnicity
- AD Patient Medical History
- AD Patient Current/Previous Treatments for AD
- AD Patient All Current Medications

Assessment Forms: These forms capture the EASI score, ISGA score, %BSA score, and topical treatment tube weight at each assessment (Baseline, 6 Week Assessment, and 12 Week Assessment). These forms will be completed electronically in REDCap during each specified assessment.

Withdrawal Form: This electronic form (REDCap) will be used to document the time and reasons for withdrawals during the study. This form will electronically capture withdrawal information for the study and submit the information directly to a secure REDCap database at the University of Rochester Medical Center.

AD Flare Medication Form: This electronic form (REDCap) will be used to document any extra medication prescribed to control an atopic dermatitis flare in a study subject. Study personnel will record the name of medication, dosage, date started, date ended, and continued for remainder of study (yes/no) for the extra medication. Subjects will remain on study unless he/she has is prescribed systemic anti-inflammatory therapy for atopic dermatitis. The treating dermatologist will manage and monitor the flare at their discretion.

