#### **5.4. Randomization**

Randomization will assign a pediatric subject to one of two topical treatments (crisaborole or tacrolimus 0.03%) at a ratio of 1:1. Randomization will use a computerized pseudorandom number generator and will employ a random block size of 4 or 6. Study personnel will obtain randomization assignment in REDCap.

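### Baseline-to-week-12 change within an arm cannot show drug effect in this design, so efficacy and superiority claims should rest on the randomised comparison alone

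*Combined protocol and SAP*

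**What the plan says.** **Entry and baseline.** Section 5.1 (Washout Period) accepts current users of tacrolimus, crisaborole or another steroid-sparing drug "if he/she agrees to discontinuation of the medication for two weeks (i.e., 14 days) prior to starting study procedures". Afterwards "the subject will return to clinic for the baseline study visit and be randomized to tacrolimus 0.03% or crisaborole". Their baseline is therefore an off-drug score, and the drug then assigned may be the one they have just stopped. Topical steroid is handled differently in Section 3.5: "If subject is taking topical steroids, subject must be on stable dose of topical steroid", with no washout.

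**Allocation.** Section 5.4 has two active arms and no vehicle or untreated arm: "Randomization will assign a pediatric subject to one of two topical treatments (crisaborole or tacrolimus 0.03%) at a ratio of 1:1". It adds that "Randomization will use a computerized pseudorandom number generator and will employ a random block size of 4 or 6" and names no stratification factor. The On-Study Form in Section 5.3 has the field "Washout Period Required (yes/no", so washout status is known for every child, but Section 11.2 gives it no role.

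**Where the conclusions rest.**
- Section 1.4 predicts that crisaborole "will significantly decrease (i.e., score change", with 5 points or more as the threshold, for itch and pain. A separate sentence predicts more improvement than on tacrolimus.
- Section 11.1 aims the sample size at a change of at least 4 from baseline to week 12. It also calls crisaborole superior if it improves PROs or caregiver burden while EASI does not differ significantly from tacrolimus.
- Section 11.2 uses ANCOVA, correlation and regression to look for changes from baseline to week 12, naming no covariates, and t-tests to compare the changes between arms.

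Section 1.2 describes AD as "a chronic inflammatory disease characterized by flares and remissions".

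**The concern.** A fall in the crisaborole arm is treated as evidence in its own right, but three things other than the assigned drug can produce one, and a fourth makes it hard to interpret.

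- Children enter with active disease (ISGA 2 or 3 and at least 3% BSA, Section 3.5), so some regression to the mean is possible.
- The disease remits without help.
- Extra flare medication is allowed while the child stays on study (Section 8).
- A child controlled on crisaborole before the trial may worsen during washout, restart crisaborole and be scored as improved on returning to the starting state.

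With no untreated arm, nothing in the before-after change tells these apart. What is at stake is an efficacy claim for crisaborole or, through the wording in 11.1, a superiority claim that no between-arm difference in PROs supports. Read literally, that wording could be satisfied by a fall in the crisaborole arm even if tacrolimus produced the same fall.

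**Working it through.** **1. The plan's own figure.** Section 11.1 gives n = 16 for 80% power, two-sided 0.05, SD 10, an effect of 5 and a score change of 4. For a paired change, n = (SD × (1.960 + 0.842) / δ)².
- δ = 5: (10 × 2.802 / 5)² = 31.4, so 32.
- δ = 4: (10 × 2.802 / 4)² = 49.1, so 50.

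A two-arm comparison would need 63 or 99 per arm. The stated 16 does not reproduce. It works for δ = 5 if the SD of change is about 5 × √16 / 2.802 = 7.1. That is a separate matter. It is used here only to set two values for the SD of change: 10 and 7.1.

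**2. What each comparison contains.** Write D for the mean drug effect in an arm and N for the mean change that would occur anyway.
- Within the crisaborole arm: expected change = D(cris) + N.
- Between arms: [D(cris) + N] − [D(tac) + N] = D(cris) − D(tac).

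N cancels between arms because washout status and background steroid are fixed before randomisation, and remission and season fall on both arms alike in expectation. It does not cancel within an arm.

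**3. False-positive rate of the within-arm test.** Inputs: D = 0, n = 20 per arm (11.1), two-sided 0.05. The test is a one-sample t with 19 df (critical value 2.093) and noncentrality N√20 / SD. N is assumed.

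| Non-drug fall N (points) | SD of change 10 | SD of change 7.1 |
|---|---|---|
| 0 | 5% | 5% |
| 1 | 7% | 9% |
| 2 | 14% | 22% |
| 3 | 25% | 43% |
| 4 | 40% | 67% |

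Fewer than 20 per arm may contribute itch and pain scores, because children under 5 complete neither measure (5.1). At 16 per arm and SD 10, falls of 2, 3 and 4 points give 12%, 20% and 32%.

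**4. How large N might be.** The documents give no washout share, relapse size or baseline-to-week-12 correlation, so these are assumptions.
- Washout: share × worsening. With 25% to 50% washed out and 3 to 8 points of worsening, 0.25 × 3 = 0.75 to 0.50 × 8 = 4.0 points. This is a ceiling, since it counts all recovery after washout as non-drug.
- Regression to the mean: (1 − r) × elevation. With r of 0.7 to 0.5 and baselines 3 to 5 points above usual, 0.3 × 3 = 0.9 to 0.5 × 5 = 2.5 points.

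The targets are 4 points (11.1) and 5 points (1.4).

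**5. Both tests in the same simulated trials.** 40,000 trials per scenario, 20 per arm, no drug effect, and a share of children whose score falls regardless of arm.

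| Share and fall | Within-arm, SD 10 | Within-arm, SD 7.1 | Between-arm, SD 10 / 7.1 |
|---|---|---|---|
| 25%, 5 points | 8% | 10% | 4.9% / 5.0% |
| 50%, 5 points | 18% | 29% | 5.3% / 5.1% |
| 50%, 8 points | 34% | 55% | 4.9% / 5.0% |

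A separate allocation simulation put the mean between-arm shift at 0.00 points.

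**6. Chance imbalance between arms.** The SE of the difference in washout share is √(2p(1−p)/20) = 0.137 for p = 0.25 and 0.158 for p = 0.5. The 95% shift runs from 1.96 × 0.137 × 3 = 0.8 to 1.96 × 0.158 × 8 = 2.5 points. The ordinary 95% half-width at SD 10 is 1.96 × 10 × √(2/20) = 6.2 points. Adding 2.5 in quadrature, as if it were not already included, gives √(6.2² + 2.5²) = 6.7, about 8% wider.

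**The case against.** The strongest reply is that the primary objective is a comparison with tacrolimus, Section 11.2 tests it between randomised arms, and the before-after change does not enter that test. This stands. A reader might infer from the mixed baselines that the crisaborole-tacrolimus difference is biased. It is not: expected bias is zero, type I error stays near 5%, and chance imbalance in washout status is already part of the standard error.

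Three further replies also stand.
- A reader might treat all recovery after washout as artefact. The documents do not show that. A child who worsens off a drug and improves on restarting it may be showing a real drug effect. By the same logic, in the zero-effect calculation the non-drug fall has to come from something other than the restarted drug. The design cannot say how much is which.
- A reader might think that continuing topical steroid inflates the fall. It does not by itself; it may lower the baseline and leave less room to improve.
- The sizes assumed have little anchor. Entry is not selected on itch or pain, ISGA is capped at 3, and Section 1.2 says that crisaborole is hard to get authorised, so prior crisaborole users may be few. Section 5.3 gives no SD for the Itch score.

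Nor is the absence of a vehicle arm a fault in itself: comparing two standard-care drugs is a legitimate choice. None of these replies rescues the before-after claims in 1.4, 11.1 and 11.2.

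**Conclusion.** The concern holds for change within an arm and for nothing wider. Such a change cannot be attributed to crisaborole, yet the plan uses it in the primary hypothesis, the sample-size target, the primary analysis and the superiority wording.

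The 14% to 40% range rests on zero drug effect, 20 per arm, an SD of change of 10 and an assumed non-drug fall of 2 to 4 points. It is higher if the SD is 7.1 and lower if fewer children contribute. It illustrates the exposure and does not forecast it. The 0.75 to 4.0 points for washout is an upper bound, not an estimate.

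For the randomised contrast, washout status affects only precision and chance balance. The point is worth acting on because a stated rule can yield a wrong conclusion and the correction is nearly free.

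**What to change.** 1. In 1.4, 11.1 and 11.2, label baseline-to-week-12 change within an arm as descriptive.
2. Rest every efficacy and superiority statement on the crisaborole-tacrolimus contrast. Reword the superiority sentence in 11.1 so that it requires a between-arm difference in the PRO concerned.
3. Estimate that contrast by ANCOVA of the week-12 score on arm, with baseline score and the washout yes/no field from the On-Study Form as covariates. Section 11.2 already names ANCOVA, so this fills in the model.
4. Show change by washout status within each arm, descriptively.

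Stratifying the randomisation by washout status is optional. With about 40 children, covariate adjustment does most of the work and remains possible after accrual has begun.

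The cost is wording plus one variable already collected. The washout covariate spends one degree of freedom (with 40 children, 40 − 4 = 36 residual instead of 40 − 3 = 37). The real price is a more modest claim: a fall in the crisaborole arm alone no longer counts as evidence of effect. No arm, washout rule or treatment rule changes.
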